Vocal cord cyst is a fluid-filled sac inside the vocal cord, with 2 subtypes: 1) Epidermoid cyst due to epithelial inclusion 2) Mucous retention cyst due to glandular ductal obstruction. Vocal cord cysts typically do not resolve with voice therapy, and are traditionally excised with microlaryngeal surgery with microflap technique or marsupialization. ^(6,7) In our previous RCT study, subgroup analysis did not show a significant difference of vocal cord cyst recurrence in both TNLS and MLS group. However, our cohort had a higher overall vocal cord cyst recurrence rate (13.8%) compared to historic cohort rate of 2.2-8.7%^(5, 8), which may be accounted by that our vocal cord cysts were ablated and marsupialized instead of removed in the TNLS group. Nevertheless, a recent case series by Gao and colleagues showed a good functional outcome of awake KTP-laser marsupialization in selected cases. ⁹ A larger cohort is warranted to compare TNLS to MLS for vocal cord cyst. Therefore, our authors would like to conduct a randomized controlled trial to compare tradition MLS surgery to TNLS, with hypothesis that TNLS would be non-inferior to traditional microlaryngeal surgery in benign laryngeal lesions, and with its additional benefits on minimization of anesthetic risks and hospital expenses, hopefully to expand its further application.

Methodology

Study setting

This is a prospective, single-cluster randomized controlled trial conducted at two tertiary referral hospitals (Prince of Wales Hospital and Alice Ho Miu Ling Nethersole Hospital, NTEC) in Hong Kong to compare the clinical and functional outcomes of office-based TNLS to traditional microlaryngeal surgery under general anesthesia for vocal cord cysts.

Eligibility criteria

All consecutive patients with vocal cord cysts interested in operative management will be screened for eligibility.

Inclusion criteria

Patients who are (i) older than 18-year-old; (ii) able to independently provide consent; and (iii) able to tolerate flexible laryngoscopy would be recruited.

Exclusion criteria

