2. Complete head and neck physical examination
3. Flexible laryngoscopy for confirmation of diagnosis, with photo documentation of site and size (in relative to length of vocal cord in full abduction)

Diagnosis would be explained to patients, and management options of conservative, microlaryngeal surgery under general anesthesia, and TNLS with their pros and cons would be discussed. Patient information sheet and informed consent are provided to facilitate the

process. Should the patient decide to participate in the study, consent of the study would be signed in the same clinic session. Patient would be informed of his randomized treatment group, and consent of the surgery would be also signed in the same section. Participation is voluntary and any study subject can decide to withdraw at any time of the study period. Upon study withdrawal, the patient will continue to receive standard treatment according to disease status.

In addition to above mentioned assessments, patient would also be assessed in a multidisciplinary voice clinic undergoing a detailed voice assessment co-organized with speech language pathologist, including Voice-Handicap Index (VHI-30), perceptual evaluation of voice, acoustic voice analysis, aerodynamic measures and laryngeal imaging.

Failure of study intervention

When patients cannot tolerate the allocated intervention, for example patients randomized to MLS group but contraindicated to general anesthesia, or patients randomized to TNLS but cannot tolerate transnasal laser surgery due to discomfort or anxiety, can crossover to other study arm. Outcomes would be analyzed by intention-to-treat principle.

Follow-up schedule

All patients would have follow-up in a multi-disciplinary voice clinic on post-op 2 weeks, 6 weeks, 3 months, 6 months and 1 year. During the postoperative follow-ups, patients are required to fill in a questionnaire and undergo voice assessments as mentioned above.

Primary outcome

The primary outcome was to compare the pre- and post-operative Voice-Handicap Index (VHI-30) of TNLS and MLS groups. The VHI-30 is a 30-item self-administered questionnaire, which has been shown to be a reliable measure for voice treatment outcome.^(10,11) It consists of three subscales, namely physical, functional and emotional. It provides an overall measurement of a person's vocal function and how it influences a person's everyday functioning and experience.

Secondary outcomes

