The secondary outcomes included other voice-related outcomes (i.e. perceptual analysis, acoustic voice analysis, aerodynamic measure, visual analog scale (VAS) on voice quality), procedure-oriented outcomes, patient-oriented outcomes and hospital costs. Perceptual evaluation of voice using the GBRAS scale, in which patients would be required to produce sustained vowel and connected speech voice samples. Two experienced speech-language pathologists blinded to the patient's information would rate the audio recordings. For acoustic voice analysis, it would be conducted using PRATT program with parameters including

jitter, shimmer, noise-to-harmonic ratio measures and cepstral peak performance. For aerodynamic measure, maximal phonation time (MPT) would be measured by instructing patients to phonate /a:/ sound for as long as possible after maximal inspiration, at a spontaneous, comfortable pitch and loudness level, for three consequent trials. In VAS, patients would be asked to self-rate their voice quality on a visual analog scale of 0 (best) to 10 (worst). Videostroboscopy would be conducted on all patients to identify any anatomical and physiological changes, which included presence of laryngeal pathology, vocal fold closure pattern, and mucosal wave pattern.

Procedure-oriented outcomes include operation time, completeness of lesion removal, complications in Clavien-Dindo classification, length of hospital stay, disease recurrence rate, and reoperation.

Patient-oriented outcomes included peri-operative throat, nose, and overall discomfort in visual analogue scale, a 10-point scale with 0 (least uncomfortable) to 10 (most uncomfortable).

Medical costs of both interventions would be also calculated respectively, including costs for inpatient hospital stay, medical staff, operating theater and consumables.

Sample size calculation

Power calculation demonstrated that with a sample size of 21 per group, a two-arm study has a power of 80% to demonstrate a non-inferiority margin 7 absolute score, with one-sided significance of 0.05 regarding the primary outcome parameter, i.e. VHI-30. The calculation was based on published data from Misono et al.¹² in which a VHI-30 score over 16 was determined as a minimal important difference. Assuming a 20% drop-out rate, at least 54 patients were required, with 27 patients in each arm.

Participant timeline

TIMEPOINT	D1	Allocation	Post-allocation		Close-out

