	Pre-op assessment	Intra-operative	Immediate post-operative	FU at 2w, 6w, 3mo, 6mo, 1y	
Enrolment					
Eligibility screen	X				
Informed consent	X				
Randomization					
MLS		X			
TNLS		X			
Assessment					
Demographics	X				
	X				
	X				
	X				
	X				
	X				
Disease					
Type of lesion	X				
Site of lesion	X				
Size of lesion	X				
FL / Videostroboscopy	X		X		X
Anaesthetic assessment					
ASA	X				
Functional assessment					
VHI30	X				X
Other secondary voice-related outcomes (MPT, Acoustic analysis etc)	X				X
Procedural data					
Operation time		X		X	
Peri-op tolerance scale		X		X	
Peri-op pain score		X		X	
Post-operative outcome					
LOS			X		
Residual lesion			X		X
Complications			X		X
Recurrence					X
Reoperation					X
Pathology					X

Randomization

Patients are randomized to receive either MLS under general anesthesia or TNLS under local anesthesia. Block randomization is used to ensure equal distribution between two treatment arms. To avoid selection bias, the blocking mechanism is designed by a third party not involved in the study, and is not disclosed to investigators. Randomization is only performed on the day of recruitment, which the recruiter shall contact the third party for the result randomized treatment group. Both the patients and the laryngologists cannot be blinded due to the nature of operation.

Statistical method

All outcome measurements will be analyzed with an intention-to-treat principle. Independent samples t-test will be used for parametric continuous variables; Mann-Whitney U test will be used for non-parametric continuous variables; chi-square test will be used for categorical variables. A p-value less than 0.05 will be considered to be statistically significant. All statistical analysis will be performed using SPSS version 26.0.

Data monitoring and confidentiality

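### The t-test named for VHI-30 by default ignores scores already collected from patients who later drop out; a repeated-measures model would use them and guard better against selective loss in the TNLS arm

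*Protocol*

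**What the plan says.** The Statistical method section of the protocol states the principle "All outcome measurements will be analyzed with an intention-to-treat principle" and then assigns tests by type of variable. For continuous outcomes: "Independent samples t-test will be used for parametric continuous variables", with Mann-Whitney U where the variable is judged non-parametric. VHI-30, the primary outcome, is continuous, so one of these two tests applies to it. The section names no other method for continuous outcomes.

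The Sample size calculation section needs 21 patients per group "to demonstrate a non-inferiority margin 7 absolute score, with one-sided significance of 0.05" and 80% power. It then adds: "Assuming a 20% drop-out rate, at least 54 patients were required, with 27 patients in each arm".

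The Follow-up schedule section says: "All patients would have follow-up in a multi-disciplinary voice clinic on post-op 2 weeks, 6 weeks, 3 months, 6 months and 1 year". Voice assessment, including VHI-30, is also done before surgery. Each patient can therefore contribute six VHI-30 scores.

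The section on failure of study intervention applies intention-to-treat to patients who cross over. The section on recruitment and consent allows withdrawal at any time and says only that standard treatment then continues.

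**The concern.** A two-sample test takes one value per patient. Applied directly at one visit, it leaves out anyone with no value there. A patient who attends up to six months and misses one year has a baseline and four post-operative scores, none of which enters a one-year t-test. On the protocol's own allowance, about 11 of 54 randomised patients could be in this position or have left earlier.

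This matters more than usual for three reasons. The aim is that "TNLS would be non-inferior to traditional microlaryngeal surgery", so losing poor TNLS results moves the estimate towards the claim. Patients are not blinded and VHI-30 is self-reported, so attendance may plausibly depend on how well the voice has recovered. The Background also raises the possibility of poor TNLS results. It reports an overall cyst recurrence of 13.8% in the earlier trial against 2.2% to 8.7% historically, and suggests that ablating rather than removing cysts in the TNLS group may explain it, although that trial found no significant difference between arms.

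**Working it through.** **Inputs from the protocol.** 21 per group, margin 7 points, one-sided alpha 0.05, power 80%, 20% drop-out, 27 per arm, five post-operative visits.

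**Assumed inputs.** A higher VHI-30 score is worse. The true difference is 0 for power and 7 (TNLS worse by exactly the margin) for the false-claim rate. The SD is not stated, so it is back-solved below. Loss by arm, and its relation to outcome, is not given and is varied.

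**The plan's own figure.** 21/0.8 = 26.25, rounded up to 27 per arm and 54 in total. This matches. Expected evaluable: 54 × 0.8 = 43.2, so about 43 analysed and 11 not.

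**Implied SD.** 7 / ((1.645 + 0.842) × √(2/21)) = 9.12 by the normal approximation, and about 9.0 with the t distribution.

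**Simple bias calculation.** Let d be the share lost in an arm and D the number of points by which those lost are worse than those who stay.

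Observed difference = true difference − d(TNLS) × D(TNLS) + d(MLS) × D(MLS)

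With 20% lost per arm, about 22 remain in each, so SE = 9.12 × √(2/22) = 2.75. At a true difference of 7, the false-claim rate is Φ((7 − observed difference)/SE − 1.645):

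| Loss pattern (20% in each arm) | Observed difference | False non-inferiority |
|---|---|---|
| Lost patients no different, or equally worse in both arms | 7.0 | 5% |
| TNLS losses worse by 5 | 6.0 | Φ(1.0/2.75 − 1.645) = 10% |
| TNLS losses worse by 10 | 5.0 | Φ(2.0/2.75 − 1.645) = 18% |
| TNLS losses worse by 16 | 3.8 | Φ(3.2/2.75 − 1.645) = 32% |
| MLS losses worse by 16 | 10.2 | Φ(−3.2/2.75 − 1.645) = 0.2% |

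The 16 is the VHI-30 minimal important difference quoted in the sample size section. The bias in that row is 0.2 × 16 = 3.2 points, or 3.2/7 = 46% of the margin.

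The bias in points does not depend on the SD, but the error rate does. At an SD of 15 (SE = 15 × √(2/22) = 4.52), the three TNLS rows become 7.7%, 11.5% and 17.4%.

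**Simulated t-test, loss driven by the score at the analysed visit** (15,000 trials per setting, 27 per arm, SD 9.12, true difference 7):

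| Loss | Mean estimate | False non-inferiority |
|---|---|---|
| None | 7.0 | 4.9% |
| Random, 20% | 7.0 | 4.8% |
| Same rule in both arms (worse score, more loss) | 6.2 | 8.8% |
| Score-dependent in TNLS only | 5.4 | 14.3% |
| Score-dependent in MLS only | 8.6 | 1.2% |

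The third row needs care. The same rule in both arms is not the same as equal loss: when TNLS is truly worse, the rule removes more TNLS patients.

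**Simulated five-visit trials, loss in TNLS driven by the previous observed score, random in MLS.**

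- SD 9, 20% missing at the last visit, correlation 0.5 and 0.7, two strengths of dependence, 1,000 trials each. The t-test gave 8.4%, 11.8%, 9.8% and 13.9% false claims, with mean differences of 5.7 to 6.2. A repeated-measures model on the post-operative scores gave 4.9%, 5.6%, 5.7% and 5.8%, with mean differences of 6.8 to 7.0. Simulation error near 5% is √(0.05 × 0.95/1000) = 0.7 points.
- A second run (SD 9.1, about 22% missing at the last visit) gave 13% to 17% for the t-test and 4% to 5% for the mixed model.
- A third run of the t-test (3,000 trials per setting, SD 9.1) gave 9% to 18%, so the upper end is not sharp.

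**Power with random loss and no true difference.** t-test 80% to 81% against about 85% for the mixed model in the first run; 78% to 80% against 83% to 84% in the second.

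**The case against.** The strongest objection is that missing-data handling is commonly left to the statistical analysis plan, which is not shown. The protocol nowhere says that patients without a value are excluded, and a t-test can follow imputation. This stands. A reader might infer that the promised intention-to-treat analysis is contradicted and turns into a completers' analysis. The documents do not support that. The protocol applies intention-to-treat to crossovers as well, and a t-test by allocated arm is compatible with it. What remains is a stated choice of test that, as written, makes no use of repeated scores the trial collects.

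A reader might also infer that the trial is biased towards TNLS. That does not follow either. The protocol gives no drop-out by arm and no link to outcome. The bias is nil under random or truly equal loss, and it reverses if MLS loses its poor results. Nor is the sample size at fault: 27 per arm is right for 20% loss, and under random loss the t-test keeps about the planned power.

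Three objections limit the size of the gain. The five-visit simulations assume loss depends on the previous observed score, which is the condition under which the mixed model works, so they favour the remedy. The gain also assumes a late primary visit; at an early one there are few earlier scores to recover. Finally, a model on post-operative scores alone leaves out patients lost before their first visit. Including baseline as a score keeps them in the model, though they then add little to the arm difference.

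**Conclusion.** The point holds as an improvement to a stated method that should be made. It is not a contradiction or an error of calculation. With 20% loss, the named test by default sets aside about 11 of 54 patients and their earlier scores. If poor TNLS results are lost more often, false non-inferiority rises from 5% to roughly 8% to 17%, depending on how strongly loss follows the score. If only MLS loses its poor results, the rate falls to about 1%. Under random loss the cost is about four or five points of power.

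These figures rest on an SD of about 9 implied by the sample size, a late analysis visit and assumed loss patterns. Confidence in the direction of the remedy is good; confidence in the exact error rates is moderate.

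**What to change.** For VHI-30, replace the t-test in the Statistical method section with a linear mixed model for repeated measures, which the named package provides.

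- Use the baseline and all post-operative scores of every randomised patient, by allocated arm, with arm, visit and arm-by-visit terms. Treat baseline as one of the repeated scores, with a common baseline mean for both arms (justified by randomisation), so that patients with only a baseline score stay in the model.
- Take the arm difference (TNLS minus MLS) at the chosen primary visit and compare its upper one-sided 95% limit with 7.
- Add one sensitivity analysis that worsens missing TNLS scores in steps, for example from 0 to 16 points, and report the step at which the conclusion changes.

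The change costs wording only: no new patients, visits or measurements, and the sample size stays at 54. It should be settled before outcome data are seen. The downside is a slightly more complex model that assumes loss depends on observed scores. The sensitivity analysis probes that assumption but does not remove it.

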Randomized controlled trial of awake transnasal laser-assisted surgery (TNLS) and microlaryngeal surgery for vocal cord cyst

CREC Ref No: 2023.644-T

Background

Office-based awake transnasal laser-assisted surgery (TNLS) has been gaining popularity in treating different laryngeal lesions, with the advantages of avoiding general anesthetic risks and minimizing healthcare-related costs. ⁽¹⁻⁴⁾ In addition, the general waiting time for surgeries under general anesthesia in public hospitals is getting longer due to the increasing population and limited resources. We have recently conducted a novel randomized controlled trial in 2021-2022 comparing the functional and cost-effectiveness of traditional microlaryngeal surgery (MLS) under general anesthesia and TNLS for benign laryngeal lesions (vocal cord polyps, nodules, cysts, granuloma and Reinke's edema), and found that TNLS was superior to MLS in terms of length of stay, intraoperative complications, perioperative throat discomfort and hospital costs; while it was equivalent to MLS in terms of functional outcome, operative time and recurrence rate. ⁽⁵⁾ However, since our previous study's main goal was to compare TNLS to MLS in a macroscopic perspective in terms of functional outcomes and cost-effectiveness, it had included a wide variety of benign laryngeal lesions, and different vocal cord lesions may respond differently to laser surgery.

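### Recurrence is judged by a chi-square difference test at p<0.05, which at 27 per arm cannot support a claim that TNLS does not recur more often; a risk difference with a 95% interval should carry that conclusion

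*Protocol*

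**What the plan says.** The Background reports that in the sponsor's earlier randomized trial "subgroup analysis did not show a significant difference of vocal cord cyst recurrence in both TNLS and MLS group". It adds that "our cohort had a higher overall vocal cord cyst recurrence rate (13.8%) compared to historic cohort rate of 2.2-8.7" (percent), and offers as a possible explanation that "our vocal cord cysts were ablated and marsupialized instead of removed in the TNLS group". It concludes that "A larger cohort is warranted to compare TNLS to MLS for vocal cord cyst", and then gives non-inferiority of TNLS as the hypothesis.

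In Secondary outcomes, recurrence is one of the procedure-oriented outcomes: "length of hospital stay, disease recurrence rate, and reoperation". The section Statistical method applies one rule to all such outcomes, "chi-square test will be used for categorical variables", and one threshold: "A p-value less than 0.05 will be considered to be statistically significant". The section Sample size calculation sets a non-inferiority margin for VHI-30 only, and the 54 patients are sized on that outcome.

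**The concern.** The clinical question about recurrence is whether TNLS is worse. The stated rule asks whether the two arms differ. In a small trial with few events these questions come apart: failing to find a difference is weak evidence that none exists, and the p-value does not show how large an excess remains possible.

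The risk of misreading is concrete. The Background summarizes the earlier trial, across all its benign lesions, as finding TNLS "equivalent to MLS in terms of functional outcome, operative time and recurrence rate", and gives no margin for recurrence. If the new trial follows its stated rule and p exceeds 0.05, a similar sentence about cysts could follow, although the data might be compatible with a substantial excess under TNLS. Recurrence is the disadvantage of TNLS that the protocol itself raises, so this would affect how far the procedure is extended.

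**Working it through.** **Inputs from the protocol.** 27 per arm, 20% drop-out, 21 per group before inflation (Sample size calculation); overall cyst recurrence 13.8%, historic range 2.2% to 8.7% (Background); chi-square at p<0.05 (Statistical method), taken as two-sided.

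**The plan's own figure.** 21 / (1 - 0.20) = 26.25, rounded up to 27 per arm, 54 in total. This reproduces. It rests on VHI-30; no power is stated for recurrence.

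**Assumed arm rates.** The protocol gives no recurrence rate by arm, so two constructions are used:

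- A: MLS has a historic rate and TNLS has 13.8%.
- B: 13.8% is the mean of two equal-sized arms, so TNLS = 2 × 13.8 - MLS. This gives 27.6 - 8.7 = 18.9%, 27.6 - 5.0 = 22.6% and 27.6 - 2.2 = 25.4%. The 5% is an assumed value inside the historic range.

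**Power.** Exact power is the sum, over all pairs of counts (x, y) with p<0.05, of Bin(x; n, p1) × Bin(y; n, p2).

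| Construction | MLS | TNLS | Chi-square, 27/arm | Chi-square, 21/arm | Fisher, 27/arm | Fisher, 21/arm |
|---|---|---|---|---|---|---|
| A | 8.7% | 13.8% | 9.5% | 7.3% | 2% | 3% |
| A | 2.2% | 13.8% | 34% | 22% | 10% | 10% |
| B | 8.7% | 18.9% | 20% | 16% | 8% | 8% |
| B | 5.0% | 22.6% | 51% | 39% | 28% | 26% |
| B | 2.2% | 25.4% | 80% | 66% | 54% | 49% |

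Chi-square power is below 50% in seven of the ten cells. Expected recurrences per arm, n × (p1 + p2) / 2, run from 21 × 0.080 = 1.7 to 27 × 0.138 = 3.7. They are below 5 throughout, so the chi-square approximation is itself weak.

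**What an interval would show (Newcombe 95%).**

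- 3/27 against 3/27. Each proportion is 11.1%, with Wilson limits 3.9% and 28.1%. The difference is 0, and the half-width is √[(11.1 - 3.9)² + (28.1 - 11.1)²] ≈ 18.4. The interval is -18 to +18 points, while p = 1.0.
- 5/27 against 1/27. Chi-square = 54 × (5 × 26 - 1 × 22)² / (27 × 27 × 6 × 48) = 3.0, p = 0.083; Fisher p = 0.19. The difference is 18.5 - 3.7 = 14.8 points, with interval -3 to +33. The observed rate is five times higher, yet the stated rule would record no significant difference.

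**The case against.** Four objections deserve weight.

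1. *Recurrence is secondary, and low power on a secondary outcome is normal.* This stands. The low power comes from sizing 54 patients on VHI-30, not from choosing chi-square, and an interval does not raise it. With 0/27 in both arms the Newcombe upper limit is already +12.5 points. The point concerns only what may be concluded.

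2. *A separate statistical analysis plan may add estimates and intervals.* It may, and naming chi-square does not exclude them. But the protocol does state a test and a threshold for recurrence, and that rule suits a difference question rather than the non-inferiority hypothesis. The point is limited to that mismatch.

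3. *The sponsor did not over-interpret the earlier cyst result.* This also stands. A reader might infer that the cyst comparison was called equivalent. That word covers all lesions in the earlier trial; for cysts the protocol reports only non-significance, draws attention to the high rate and asks for a larger cohort. Nor does it name the earlier trial's test.

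4. *Recurrence is not the sole reason for a cyst-only trial.* Correct. The Background also says that lesion types may respond differently to laser.

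A reader might further infer that a time-to-event analysis is required. The documents do not support that: recurrence is assessed at five scheduled visits, so the gain would be small, and the protocol does not fix how incomplete follow-up enters the rate.

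**Conclusion.** The point holds in limited form. The rule stated for recurrence is a difference test, and at 27 per arm (about 21 evaluable) a non-significant result cannot support a statement that TNLS recurs no more often than MLS. Under the assumed arm rates, chi-square power is between about 7% and 80%. Equal observed rates of 11.1% would still leave an excess of about 18 points within the 95% interval.

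It is tempting to conclude that the trial will most likely end in another non-significant comparison. The documents do not support that prediction: it depends on arm rates they do not give, and at 2.2% against 25.4% power is 80% with 27 per arm and 66% with 21. The conclusion above does not depend on the prediction. It rests on the width of the interval at this sample size.

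The change is worth making because recurrence is the drawback of TNLS that the protocol suspects. It does not touch the primary analysis.

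**What to change.** In Statistical method, add for recurrence and reoperation at 1 year:

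- The main result is the TNLS minus MLS risk difference with a 95% interval, for example Newcombe's on the observed counts, with the number not followed to 1 year stated for each arm.
- Any hypothesis test is a supplement, using Fisher's exact test where expected counts are below 5.
- A non-significant p-value will not be described as equivalent, or as recurrence that is not higher.

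No formal recurrence margin is needed, and at this sample size one would seldom be met. The cost is analysis wording on outcomes already planned, with no added patients or visits. The downside is a less favourable, probably inconclusive, statement on recurrence.

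### Read literally, the test rule sends the ordered complication grade to a chi-square test that ignores order: a minor, cheap fix to secondary analyses only

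*Protocol*

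**What the plan says.** Protocol, Statistical method, sets rules for all outcome measurements and sorts them by type of variable. Parametric continuous variables get an independent-samples t-test. For the rest, "Mann-Whitney U test will be used for non-parametric continuous variables" and "chi-square test will be used for categorical variables". The threshold is given once: "A p-value less than 0.05 will be considered to be statistically significant". No outcome is tied by name to a test, and ordinal variables are not mentioned.

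Protocol, Secondary outcomes, lists at least one ordered outcome, "complications in Clavien-Dindo classification", among the procedure-oriented outcomes. It also lists "Perceptual evaluation of voice using the GBRAS scale", rated from recordings by two blinded speech-language pathologists. The number of levels is not stated, nor whether ratings are summed, averaged over raters or taken item by item.

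Protocol, Sample size calculation, sizes the trial for VHI-30 alone, on a "non-inferiority margin 7 absolute score" at "one-sided significance of 0.05".

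**The concern.** A complication grade is not a continuous measurement, so under these three rules its literal home is the chi-square test. Pearson's statistic is the same however the grade labels are shuffled. A steady drift towards worse grades in one arm therefore counts no more than an irregular scatter of the same size. The test spends k − 1 degrees of freedom on what is usually a one-direction question. A test that uses the order is already named in the same section, but its wording reserves it for continuous variables.

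The two outcomes are not trivial here. The Background says that the group's previous trial found an advantage of TNLS on intraoperative complications. The perceptual rating is the only voice outcome that the Protocol says is rated blind, and neither patients nor surgeons can be blinded. In a trial with a non-inferiority hypothesis, a non-significant secondary result is easily read as reassurance, so the test should not be weaker than it needs to be.

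**Working it through.** **Inputs from the Protocol.** 21 evaluable patients per arm, 20% drop-out, 27 per arm, 54 in total (Sample size calculation); significance at 0.05 (Statistical method).

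**The plan's own figure.** 21 / (1 − 0.20) = 26.25, rounded up to 27 per arm; 2 × 27 = 54. This reproduces. The 21 per arm is taken as given, because no standard deviation is stated.

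**Assumptions, none of them in the Protocol.** Two-sided 0.05 for secondary comparisons; three to five grades; the control distributions shown in the table; a proportional-odds shift, in which the odds of lying above each cut-point are multiplied by the odds ratio (OR) in one arm.

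**Formulas.** With a_j and b_j the counts in grade j, t_j = a_j + b_j, n per arm and N = 2n:

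- Chi-square: X² = Σ [(a_j − t_j/2)² + (b_j − t_j/2)²] / (t_j/2), on (non-empty grades − 1) degrees of freedom. The sum does not change if the grades are reordered.
- Mann-Whitney: W = Σ a_j m_j, with m_j the midrank of grade j; mean n(N + 1)/2; variance (n²/12)[(N + 1) − Σ(t_j³ − t_j)/(N(N − 1))]; normal approximation.

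**Simulated power, chi-square / Mann-Whitney in %, with the gap in points** (20,000 replicates for the four-level rows, 100,000 for the others):

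| Control distribution, % | n per arm | OR 2 | OR 3 |
|---|---|---|---|
| 35/35/20/10 | 21 | 14.4 / 22.8 (8.4) | 32.3 / 48.2 (15.9) |
| 35/35/20/10 | 27 | 18.4 / 28.7 (10.3) | 41.3 / 59.0 (17.7) |
| 80/12/5/3 | 21 | 7.5 / 16.1 (8.6) | 20.1 / 36.7 (16.6) |
| 80/12/5/3 | 27 | 10.3 / 19.7 (9.4) | 27.0 / 45.5 (18.5) |
| 90/7/2/1 | 21 | 4.1 / 10.9 (6.8) | 10.4 / 24.0 (13.6) |
| 90/7/2/1 | 27 | 5.7 / 13.6 (7.9) | 15.0 / 30.2 (15.2) |
| 70/15/8/4/3 | 21 | 8.3 / 19.6 (11.3) | 21.2 / 43.4 (22.2) |
| 70/15/8/4/3 | 27 | 11.0 / 23.9 (12.9) | 29.4 / 52.8 (23.4) |
| 40/40/20 | 21 | 17.3 / 21.8 (4.5) | 37.2 / 46.1 (8.9) |
| 40/40/20 | 27 | 21.3 / 27.3 (6.0) | 46.7 / 57.0 (10.3) |

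With four or five grades the gap is about 7 to 13 points at OR 2 and 14 to 23 at OR 3. With three grades it is about 5 to 6 and 9 to 10. A fair summary is roughly 6 to 13 and 10 to 23. The linear-by-linear trend test came within about 6 points of Mann-Whitney in every four-level scenario.

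**Size when the arms do not differ.** For the two sparse four-level distributions, chi-square rejects in 1.2% to 2.5% of trials and Mann-Whitney in 3.9% to 5.1%, against a nominal 5%. In every simulated table from those two distributions, more than 20% of cells had an expected count below 5. For 35/35/20/10, both tests are close to 5%.

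**How large the assumed effect is.** With 70/15/8/4/3, 30% of controls have some complication. The odds are 0.30/0.70 = 0.43; three times that is 1.29; 1.29/2.29 = 56%. So OR 3 means a rise from 30% to 56%.

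**The case against.** The strongest reply is that the Protocol never says that ordered scores count as categorical. Which class they belong to is open, and matching tests to individual secondary outcomes is ordinary SAP content. Much of this stands for the perceptual ratings. A summed or averaged rating can be treated as a non-parametric score, for which Mann-Whitney is already named. A reader might infer that the Protocol commits these ratings to chi-square; it does not.

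For Clavien-Dindo grade the reply is weaker, because a complication grade cannot well be called continuous and the rule is stated for all outcomes. The text is not silent on tests; it gives a rule that fits this outcome poorly. Even so, the Protocol does not say that the grade will be compared as a table with several levels. If complications are reduced to any against none, or split at a chosen grade, an order-blind test loses nothing.

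A reader might also infer that the trial loses power it was designed to have. It does not: the 54 patients are sized for VHI-30 only. Nor does the better test rescue these comparisons. At OR 2 with 27 per arm, Mann-Whitney reaches only about 14% to 29% in the scenarios above, so a non-significant result is likely with either test. An OR of 3 is a large effect that no figure in the Protocol supports. Finally, a conservative chi-square test does not create false positive claims; it only makes true differences harder to see.

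It is also tempting to add stroboscopy. The Protocol names presence of pathology, closure pattern and mucosal wave pattern, and describes none of them as graded, so chi-square may be right for them.

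**Conclusion.** The point holds as a minor one about secondary analyses. Taken at its word, the test rule sends Clavien-Dindo grade, and perceptual ratings if analysed as item grades, to a test that discards their order and is conservative with sparse grades. The cost is the 6 to 13 points (OR 2) and 10 to 23 points (OR 3) shown above. Those figures rest wholly on assumed distributions, an assumed number of levels, a two-sided 0.05 and a shift in one direction; a three-level scale at 21 per arm falls slightly below both ranges. The primary VHI-30 comparison, the sample size and the non-inferiority conclusion are untouched.

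**What to change.** Add one sentence to the Statistical method, before outcome data are examined, to this effect: ordered categorical outcomes (Clavien-Dindo grade when compared as a grade, and perceptual ratings) will be compared between arms with the tie-corrected Mann-Whitney U test or the linear-by-linear trend test, in an exact version where the table is sparse; chi-square is kept for binary and unordered outcomes, including stroboscopy patterns unless they are scored on an ordered scale. Choose one of the two tests when writing it, so that no choice is left for after the data are seen.

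The cost is a sentence, and sample size and data collection do not change. There are two small downsides. A rank or trend test is less sensitive to a difference that does not run in one direction across the grades. And the power figures above are for the normal approximation, so an exact version may keep somewhat less of the gain.
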